6.9 Early Withdrawal/Termination Visit

Early withdrawal visit procedures will be performed for participants who received study treatment and who withdrew from the study prior to Day 57. Collect as much of the safety data as possible. If a subject tests positive for SARS-CoV-2 during the study and a subject withdraws prior to Day 57, collect as much safety data as possible while reducing the risk of transmission and following local rules and regulations.

If the participant withdrew consent, the PI must get participant agreement to perform the early withdrawal assessments and document this agreement in the source documents.

Perform the following in-clinic or via telemedicine follow-up:

- Assessment of AEs and concomitant medications.
- Targeted physical exam, if clinically indicated.
- If WOCBP, confirm use of contraceptives.
- Provide counseling to participants on precautions/measures to prevent contracting SARS-CoV-2 infection.
- Only if participant becomes positive for SARS-CoV-2: assess clinical status based on an Ordinal Outcome Scale ([Appendix II](#)). Perform assessments via telemedicine if possible.

In-clinic staff or home healthcare attendant to perform the following:

- Serum sample for SARS-CoV-2 antibody PK assessment.
- Safety laboratory assessments:
 - Blood sample for Chem 7 panel, total and direct bilirubin, ALT, AST, LDH, CBC with differential) if clinically indicated (as per investigator's discretion during in-clinic or telemedicine follow-up).
 - Sample for urinalysis if clinically indicated (as per investigator's discretion during in-clinic or telemedicine follow-up).

Anti-SARS-CoV-2 Immunoglobulin Intravenous (Human) (NP-028), abbreviated as COVID-HIG
EBS-CVH-006, Version 3.0, 18 Feb 2022

- Blood sample for viral marker testing (HIV 1/2 antibody, HBV surface antigen, HCV antibody).
- Vital signs (resting ≥ 10 minutes) [body temperature, blood pressure (seated), pulse, SpO₂ (pulse oximetry) and respiratory rate]. Note: perform only if clinically indicated (as per investigator's discretion).
- Nasopharyngeal swab sample for SARS-CoV-2 RT-PCR, if clinically indicated (as per investigator/sub-investigator's assessment).

7 ASSESSMENT OF PHARMACOKINETICS

In this study, only pharmacokinetic assessments will be performed to evaluate study objectives. The assessments described below will be used to derive serum concentrations of SARS-CoV-2 antibodies (by testing PK samples with a validated immunobinding IgG assay) that will be used to calculate the PK parameters.

7.1 Description of Study Assessments

Assessments that will be performed according to standard practices as scheduled in the Schedule of Events are not described further in this section. The visit time points of these procedures and assessments can be found in the Schedule of Events ([Table 2](#)).

Specific procedures related to collection, processing, storage, and shipment of the samples are provided in the Laboratory Manual. For the timing of sample collection refer to the Schedule of Events ([Table 2](#)).

7.1.1 Efficacy Outcomes

Not applicable.

7.1.2 Pharmacokinetic Samples

Serum samples will be collected as described for all participants for PK analyses as described in Section [7.3](#). For duration of sample retention see Section [12.6](#).

All serum samples must be taken as closely as possible to the specified times in relation to the start of IP administration (visit windows provided in Section [6](#)).

Refer to the Laboratory Manual for information regarding samples to be collected and tests to be completed.

7.1.3 Nasopharyngeal Samples

Nasopharyngeal swabs will be used to collect samples from the nasopharynx to measure if the participant is infected with SARS-CoV-2. Nasopharyngeal swab samples for SARS-CoV-2 RT-PCR test will be collected at Screening, Day -1, Day 8, Day 15, Day 29, Day 43, Day 57, and as clinically indicated (as per investigator/sub-investigator's assessment of the participant in-clinic or during the telemedicine follow-up) and tested by the Phase 1 unit.

Anti-SARS-CoV-2 Immunoglobulin Intravenous (Human) (NP-028), abbreviated as COVID-HIG
EBS-CVH-006, Version 3.0, 18 Feb 2022

7.1.4 Non-standard Safety Outcomes

There are no non-standard safety outcomes.

7.2 Specification of the Outcome Measures

Blood will be drawn to collect serum to measure SARS-CoV-2 antibodies and for safety laboratory assessments.

Refer to the Laboratory Manual for information regarding samples to be collected and tests to be completed.

7.3 Methods and Timing for Assessing and Recording of Outcome Measures

Pharmacokinetic parameters of COVID-HIG administered IM, SC, or IV as a single dose will be determined in healthy adults (see Section 9.4.2). The samples drawn at the time points described below will be used to derive serum concentrations of SARS-CoV-2 antibodies (by testing PK samples with a validated immunobinding IgG assay) that will be used to calculate the PK parameters. The immunobinding IgG assay will be performed at the facility outlined in the EBS-CVH-006 Laboratory Manual.

Analysis of PK will include PK sample test results (from samples collected by assigned site staff) from pre-dose on Day 1 and post-dose timepoints at Day 1: 1 hour (± 10 mins), 2 hour (± 15 mins), 4 hour (± 15 mins), 8 hour (± 30 mins) and 12 hour (± 30 mins) post-infusion. In addition, the following post-dose timepoints will be included (brackets indicate days after injection on Day 1): Day 2 (1 ± 0.5 days), Day 3 (2 ± 0.5 days), Day 4 (3 ± 0.5 days), Day 6: (5 ± 0.5 days), Day 8 (7 ± 1 day), Day 15 (14 ± 2 days), Day 29 (28 ± 2 days), Day 43 (42 ± 3 days), and Day 57 (56 ± 3 days). The IV arm (Arm 3) will not have data for post dose samples on Day 3 or Day 6 as these will not be collected.

8 SAFETY ASSESSMENTS AND REPORTING

The safety of COVID-HIG will be assessed by collection of AEs, laboratory test results (blood chemistry and hematology, urinalysis), concomitant medications, vital signs, and physical exam results.

The occurrence of AEs will be monitored throughout all phases of the study and will cover all participating subjects. Any medical history changes that occur after screening but before dosing will be captured as an AE. Any AE that occurs after screening but before dosing will be documented in the source documents and captured in EDC if subject is randomized. Capture of treatment emergent adverse events (TEAEs) starts from the time of COVID-HIG administration and until the end of study period (up to Day 57 visit). Unanticipated problems related to study procedures may be collected following enrollment.

Adverse events are to be elicited by the investigator (or designate) by asking the participant non-leading questions. The association of the AE to COVID-HIG is to be judged by the investigator as related or unrelated (see Section 8.1.9 below).

Anti-SARS-CoV-2 Immunoglobulin Intravenous (Human) (NP-028), abbreviated as COVID-HIG
EBS-CVH-006, Version 3.0, 18 Feb 2022

8.1 Definitions

8.1.1 Adverse Event

An AE is any untoward medical occurrence in a patient or clinical investigation subject administered a pharmaceutical product and that does not necessarily have a causal relationship with this treatment. An AE can therefore be any unfavourable and unintended sign (including an abnormal laboratory finding), symptom, or disease temporally associated with the use of a medicinal (investigational) product, whether or not related to the medicinal (investigational) product.

Notes:

- *A diagnosis should be captured as an adverse event term and signs and symptoms should be captured only in the absence of a unifying diagnosis. If a diagnosis is ultimately made, it should replace the previous report based on signs and symptoms.*
- *In the event that there are multiple diagnoses, then all diagnoses should be captured.*
- *The worsening of an existing sign, symptom or disease is also considered to be an AE.*
- *An abnormal laboratory finding deemed by the PI (or designee) as not clinically significant will not be captured as an AE, but an abnormal laboratory finding that worsens after dosing with the investigational product, from not clinically significant to clinically significant, is considered an AE.*
- *Surgical procedures are not AEs. They are the action taken to treat a medical condition. Interventions that were planned prior to study entry for medical conditions that started prior to study entry but did not worsen during the clinical study are not reported as AEs.*

8.1.2 Serious Adverse Event

An SAE is any untoward medical occurrence that: results in death, is life threatening, requires inpatient hospitalization or prolongation of existing hospitalization, results in persistent or significant disability/incapacity or substantial disruption of the ability to conduct normal life functions, or is a congenital anomaly/birth defect.

Important medical events which may not result in death, be life threatening, or require hospitalization may be considered an SAE when, based upon appropriate medical judgment, they may jeopardize the patient or subject and may require medical or surgical intervention to prevent one of the outcomes listed in this definition.

Notes:

- *Death is an outcome and not an event. The condition leading to death is the event. If no other information regarding the cause of death is available, the event will be considered “Unspecified Adverse Event”.*
- *Overnight stays at hospital/clinic that occurs during a trial for social reasons (e.g., transportation difficulties, respite care) is not considered to be a hospitalization event.*

Anti-SARS-CoV-2 Immunoglobulin Intravenous (Human) (NP-028), abbreviated as COVID-HIG
EBS-CVH-006, Version 3.0, 18 Feb 2022

8.1.3 Adverse Drug Reaction

A response to a medicinal product which is noxious and unintended [DIR 2001/83/EC Art 1(11)]. Response in this context means that a causal relationship between a medicinal product and an AE is at least a reasonable possibility (see Annex IV, ICH-E2A Guideline).

8.1.4 Suspected Unexpected Serious Adverse Reaction

Suspected Unexpected Serious Adverse Reaction (SUSAR) is the term used to refer to an AE that occurs in a clinical trial subject, which is assessed by the Sponsor and or PI as being unexpected, serious and as having a reasonable possibility of a causal relationship with the IP.

8.1.5 Adverse Events of Special Interest

Adverse events of special interest (AESIs) are AEs (serious or non-serious) that are of scientific and medical concern specifically related to the sponsor's product or program for which ongoing monitoring and rapid communication by the investigator to the sponsor may be appropriate. Such events may require further investigation in order to characterize and understand them. In this study, there are no AESIs.

8.1.6 Solicited Adverse Event(s)

A solicited adverse event (solicited AE) is a protocol-specified AE about which the PI (or designee) proactively asks the subjects during a protocol-specified time period. There are no solicited adverse events in this study.

8.1.7 Unsolicited Adverse Event

An unsolicited adverse event (unsolicited AE) is an AE that is spontaneously reported by the subject or discovered by the PI. Any newly reported/identified AE following dosing or an increase in the severity/frequency of a previously reported condition prior to dosing regardless of causal relationship with investigational product or procedure is considered an unsolicited/spontaneous event.

8.1.8 Severity of Adverse Events

All AEs (clinical and laboratory abnormalities) irrespective of relationship to study treatment, including those that are not of a serious nature and those that are expected, will be documented by the investigators (or designate) in the source documents and appropriately recorded on AE eCRF. All AEs will be examined by the investigator or sub-investigator(s) for assessment of AE severity using the DAIDS Table for Grading the Severity of Adult and Pediatric Adverse Events (see [Appendix I](#)). For AEs that are not included in the DAIDS AE Grading Table, use the following generic scale is:

Anti-SARS-CoV-2 Immunoglobulin Intravenous (Human) (NP-028), abbreviated as COVID-HIG
EBS-CVH-006, Version 3.0, 18 Feb 2022

Table 5 Generic AE Grading Scale

Grade 1 (mild)	Mild symptoms causing no or minimal interference with usual social & functional activities with intervention not indicated
Grade 2 (moderate)	Moderate symptoms causing greater than minimal interference with usual social & functional activities with intervention indicated
Grade 3 (severe)	Severe symptoms causing inability to perform usual social & functional activities with intervention or hospitalization indicated
Grade 4 (potentially life-threatening)	Potentially life-threatening symptoms causing inability to perform basic self-care functions with intervention indicated to prevent permanent impairment, persistent disability
Grade 5 (death)	Death

8.1.9 Causality of Adverse Events

The PI is responsible for the assessment of the causality of an adverse event and the Sponsor's MM will also assess SAE causality, independent of the PI.

The following guidelines are provided for this assessment.

- **Unrelated:** No relationship between the investigational product and the reported event
- **Possibly related:** The event follows a reasonable temporal sequence from the time of administration of investigational product and/or follows a known response pattern to the investigational product but could also have been produced by other factors.
- **Probably related:** A reasonable temporal sequence of the event with administration of IP exists and based on the known response to the investigational product, known or previously reported adverse reactions to the IP or similar products, or in the PI's (or designee) clinical judgment the association of the event with the IP seems likely.
- **Definitely related:** A clinical event, including laboratory test abnormality, occurring in a plausible time relationship to IP administration, and which cannot be explained by concurrent disease or other drugs or chemicals (e.g., injection site pain, anaphylaxis, TRALI). The response to withdrawal of the IP (DECHALLENGE) should be clinically plausible. The event must be definitive pharmacologically or phenomenologically, using a satisfactory RECHALLENGE procedure if necessary.

When possible, de-challenge and re-challenge should be considered to assess the causality of the relationship between the AE and the IP.

If the relationship between the AE and the IP is determined to be "possible" or "probable," the event will be considered to be "related" to the investigational product, otherwise it will be considered "not related" for reporting purposes.

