will be followed until they complete their last scheduled follow-up visit (via telemedicine). Participants who test positive for SARS-CoV-2 will be excluded from PK analyses. As such, all subsequent visits should be done via telemedicine following SARS-CoV-2 positive status (except the Day 57 or the withdrawal visit), unless an in-person visit is deemed clinically necessary by the PI. Any in-person visits should be scheduled in a manner that reduces the risks of SARS-CoV-2 transmission, according to local rules and regulations. As the Day 57 or withdrawal visit necessitates in-person safety assessments, this visit should proceed in-person, if possible. If a participant tests positive for SARS-CoV-2 immediately prior to or at the in-person Day 57 visit, reasonable efforts will be made to collect as many of the required samples from the Day 57 visit in a manner that reduces the risk of SARS-CoV-2 transmission, according to local rules and regulations.

For details on schedule of events, refer to [Table 2](#) Schedule of Events.

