3.2.3 Safety Endpoints

3.2.3.1 Primary Safety Endpoints

The following primary safety endpoints will be evaluated:

- AEs within 72 hours post-dosing.

Anti-SARS-CoV-2 Immunoglobulin Intravenous (Human) (NP-028), abbreviated as COVID-HIG
EBS-CVH-006, Version 3.0, 18 Feb 2022

- AEs and SAEs in healthy adults up to 56 days post- administration of a single COVID-HIG dose.

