9.4.2 Pharmacokinetic Analyses

Pharmacokinetic parameters will be estimated using standard non-compartmental methods (i.e., log-linear trapezoidal method). Subjects will be stratified based on their SARS-CoV-2 detectable antibody status ($>\text{LLOQ}$, but $\leq 80 \text{ AU/mL}$ on the Diasorin LIAISON SARS-CoV-2 S1/S2 IgG assay) and undetectable antibody ($\leq \text{LLOQ}$) at screening, with analyses done by antibody status (if possible) and overall per each arm. Actual times and not nominal times will be used in the analysis; concentrations at nominal time points may be imputed using linear interpolation. Participants with elevated baseline levels of SARS-CoV-2 antibodies or participants with inadequate number of PK time points (e.g., no pre-dose sample, or no measurable post-dose sample) may be excluded from the PK analysis. Outliers will be examined for possible exclusion from analysis, such as spiking antibody levels during the study attributed to active infection. Baseline subtraction may be employed, if necessary and where possible, using the mean of individual subject's pre-dose antibody titers. For partial AUCs through a given time point, the partial AUC will be set to missing unless an actual time point occurs within $\pm 10\%$ of the nominal timepoint for a given profile.

Bioavailability will be compared between administration routes, if data permit. An ANOVA model will be used with $\text{AUC}_{0-\text{inf}}$ as the dependent variable and administration route as the fixed effect. The adjusted least square means will be used to estimate ratios of $\text{AUC}_{0-\text{inf IM}} / \text{AUC}_{0-\text{inf IV}} * 100\%$, $\text{AUC}_{0-\text{inf SC}} / \text{AUC}_{0-\text{inf IV}} * 100\%$, and $\text{AUC}_{0-\text{inf IM}} / \text{AUC}_{0-\text{inf SC}} * 100\%$ along with

Anti-SARS-CoV-2 Immunoglobulin Intravenous (Human) (NP-028), abbreviated as COVID-HIG
EBS-CVH-006, Version 3.0, 18 Feb 2022

corresponding two-sided 90% CIs calculated based on the ANOVA. The width of the 90% CIs will be examined relative to the standard of [80%, 125%] for comparative bioavailability. If the area extrapolated from the time of the last measured concentration to infinity is greater than 40% of the total AUC for a subject profile, then the observation will be excluded from bioavailability analyses. No adjustment for multiplicity will be applied, and no formal hypothesis testing will be performed.

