9.4.3 Safety Analyses

9.4.3.1 Study Medication Exposure

Participant exposure to study medication (amount administered and administration per protocol yes/no) will be tabulated for the safety population by administration route and by baseline antibody level.

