9.4.3.2 Adverse Events and Serious Adverse Events

Treatment-emergent adverse events are defined as AEs that present after the initiation of study IP or any AEs already present that worsen in either intensity or frequency following treatment. The incidences of TEAEs and SAEs will be summarized by administration route for the PK population using the MedDRA coded terms for SOC and PT and by event severity.

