9.4.3.3 Clinical Laboratory Test Results

Hematology and clinical chemistry laboratory test results and change from baseline to Day 2 and Day 4 will be summarized by time point and administration route for the safety population. The clinical significance of any abnormality will be assessed by the investigator. Abnormal laboratory results will be graded with severity grade 1 to 4 (grade 1=mild, through grade 4=potentially life-threatening) according to the DAIDS Table for Grading the Severity of Adult and Pediatric Adverse Events ([Appendix I](#)). Values within the normal range as well as out of range laboratory values not meeting criteria for severity of at least grade 1 will be considered grade 0. Shift tables of laboratory abnormalities (Low, Normal, High) and/or severity grade (0,

Anti-SARS-CoV-2 Immunoglobulin Intravenous (Human) (NP-028), abbreviated as COVID-HIG
EBS-CVH-006, Version 3.0, 18 Feb 2022

1-2, ≥ 3) will be provided for selected laboratory parameters summarized by time point and administration route for the safety population.

Results for urinalysis, pregnancy tests, and viral markers will be listed by participant.

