9.5 Analysis Populations

Analysis will be based on the following study populations:

Safety Population: All randomized participants who receive any amount of COVID-HIG IM, COVID-HIG SC, or COVID-HIG IV, analyzed according to the actual study treatment arm.

PK Population: All participants who are randomized and received COVID-HIG IM, COVID-HIG SC, or COVID-HIG IV according to the protocol and with evaluable PK data (i.e., no major protocol deviations affecting PK sampling and results including COVID-19 infection, adequate number of PK sample test results), analyzed according to actual study treatment arm.

Anti-SARS-CoV-2 Immunoglobulin Intravenous (Human) (NP-028), abbreviated as COVID-HIG
EBS-CVH-006, Version 3.0, 18 Feb 2022

SARS-CoV-2 Positive Population: Any randomized participant (whether or not dosed with COVID-HIG) who tests positive for SARS-CoV-2 during the study period and for whom data are available, analyzed according to randomized study treatment arm. This population is used for the COVID-19 symptom severity exploratory endpoint.

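### Two protocol safety rules are wrong as written, though the SAP has both right: definitely related AEs count as not related, and the AE table uses the PK population

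*Protocol*

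**What the plan says.** **Causality.** Protocol 8.1.9 sets out four levels: unrelated, possibly related, probably related and definitely related. It then reduces them to two for reporting purposes. When the relationship is judged "possible' or 'probable,' the event will be considered to be 'related' to the investigational product, otherwise it will be considered 'not related". Protocol section 8 asks the investigator for a related or unrelated judgement and refers back to 8.1.9 for it. SAP 6.3 defines a related AE as one judged possibly, probably or definitely related.

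**Population for adverse events.** Protocol 3.2.3.1 lists "AEs and SAEs in healthy adults up to 56 days" after dosing among the primary safety endpoints. Protocol 9.4.3.2 states: "The incidences of TEAEs and SAEs will be summarized by administration route for the PK population". Elsewhere in 9.4.3 the population is different. Exposure "will be tabulated for the safety population by administration route and by baseline antibody level", and laboratory results "will be summarized by time point and administration route for the safety population". Vital signs (9.4.3.4) and swab results (9.4.3.5) also use the safety population.

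Protocol 9.5 defines the safety population as everyone randomised who received any amount of product. The PK population is narrower. It requires dosing in line with the protocol and evaluable PK data, explained as "no major protocol deviations affecting PK sampling and results including COVID-19 infection, adequate number of PK sample test results". Protocol 3.1 adds: "Participants who test positive for SARS-CoV-2 will be excluded from PK analyses".

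SAP 5.2, 9 and 9.2.1 put all safety data, including the AE summary, in the Safety population.

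**The concern.** Both protocol sentences give a wrong result if they are followed.

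For causality, the word 'otherwise' sends every level not named to the unrelated side, and the definite level is not named. The protocol's own examples of that level are injection site pain, anaphylaxis and TRALI. Injection site pain is a realistic event here, because two of the three arms are IM and SC and section 1.3.1 lists local injection reactions among the most common. The SAP governs the analysis tables but does not amend the protocol's reporting classification.

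For the AE table, membership of the PK population depends partly on what happens after dosing. A participant who becomes infected, has too few PK results, or is not dosed according to the protocol could drop out of the table for a primary safety endpoint. The last group might include someone whose injection was halted for an AE, yet the synopsis lists AEs leading to discontinuation or suspension of administration as a primary endpoint. Infection is a practical possibility, since the study was truncated because of omicron's effect on enrollment and retention.

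At stake are a correct relatedness label and a complete safety denominator. A reader comparing the two documents also finds two unexplained differences.

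**Working it through.** The plan gives no figure to reproduce on this point, so the check is mainly a comparison of texts.

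**Step 1. Put each causality level through both rules.**

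| Level (protocol 8.1.9) | Protocol 8.1.9 rule | SAP 6.3 rule |
|---|---|---|
| Unrelated | not related | not related |
| Possibly related | related | related |
| Probably related | related | related |
| Definitely related | **not related** | related |

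The protocol counts 2 of 3 positive levels as related and the SAP counts 3 of 3. The rules differ only at the definite level.

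**Step 2. Look for protocol text that corrects the rule.** Section 8 points back to 8.1.9. The pregnancy text in 8.3.1 has its own causality wording but covers only SAEs associated with a pregnancy. No other general rule was found.

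**Step 3. See what depends on the label.**

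- All AEs are recorded whatever their relationship (8.1.8).
- All SAEs go to the sponsor within 24 hours (8.3.1).
- The SAE pause criterion ignores relatedness (8.5).
- SUSARs turn on a reasonable possibility of causation (8.1.4).
- Unanticipated problems have their own wording (8.4.4).

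AE and SAE counts therefore do not change, and no expedited-reporting failure follows.

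**Step 4. List the population named in each part of protocol 9.4.3.**

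| Subsection | Output | Population |
|---|---|---|
| 9.4.3.1 | Exposure | safety |
| 9.4.3.2 | TEAEs and SAEs | **PK** |
| 9.4.3.3 | Laboratory tests | safety |
| 9.4.3.4 | Vital signs | safety |
| 9.4.3.5 | Swab results | safety |

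Four of five use the safety population. The exception is the subsection that carries a primary endpoint.

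**Step 5. Size of the population difference.** Inputs are 7-8 participants per arm and 23 in total, both randomised numbers (protocol 9.1). Share lost per excluded participant = 1 / n:

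- arm of 8: 1/8 = 12.5%
- arm of 7: 1/7 = 14.3%
- whole study: 1/23 = 4.3%

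The number excluded cannot be derived from the documents. Protocol 3.1 is categorical about participants who test positive. Section 9.4.2 is softer: "Outliers will be examined for possible exclusion from analysis, such as spiking antibody levels during the study attributed to active infection". That sentence concerns outlying antibody values rather than membership of the population, so it does not settle the count.

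**Step 6. See whether the SAP records the differences.** The SAP says it is based on protocol version 3.0 of 18 February 2022, and it was approved on 11 May 2022. It does note changes made by Protocol Amendment 3.0, such as follow-up shortened from 84 to 56 days (2.2 and 3.3) and the removed neutralization assay (3.1.1). No section says that it departs from protocol 8.1.9 or 9.4.3.2.

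**The case against.** The strongest reply is that nothing planned will change. Protocol section 9 describes itself as a summary and leaves the details to the SAP. The SAP is the later document and is right on both points. No reporting pathway in the protocol can be shown to use the two-way label in 8.1.9. The intent is also obvious, since a category named definitely related was hardly meant to count as unrelated. On this view both are drafting slips already corrected where it counts.

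Most of this stands, and it is why the point is minor. It does not remove the point. Section 8.1.9 is an operative rule stated to be for reporting purposes, it lies outside the statistical section that defers to the SAP, and section 8 directs investigators to it. A correct SAP limits the harm of the protocol sentence but does not amend it.

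Two further objections have some force. The percentages in Step 5 use randomised numbers, whereas an AE table counts dosed participants, whose number is not stated. They are therefore illustrative. The SAP also describes enrollment in the past tense, so there may be no further protocol amendment. In that case a note in the SAP or study report is the realistic remedy.

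**Conclusion.** Both parts hold, and the point is minor. In the protocol, one of three positive causality levels carries the wrong label, and one of five safety subsections names the wrong population for a primary safety endpoint. If the protocol text were followed, each participant outside the PK population would take about 12.5% to 14.3% of an arm out of the AE table, assuming that all 7-8 randomised per arm were dosed. How many would go is unknown.

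The effect on tables built from the SAP is none. This rests on the SAP being followed as written; the table shells and the study report were not available to check. What remains is a mislabelled category in the protocol and two unrecorded differences between the documents.

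**What to change.** At the next protocol amendment:

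1. In 8.1.9, count possible, probable and definite as related.
2. In 9.4.3.2, replace the PK population with the safety population.

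Protocol 13.2 generally requires a formal amendment for protocol changes, so these two corrections should travel with one made for other reasons. If none follows, add two lines to the SAP or the study report. They should say that definitely related events are counted as related, and that TEAEs and SAEs are summarised in the Safety population, in each case departing from the protocol text.

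The cost is two wording corrections or two lines of text, with no new data or analyses.
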